### **Data analytic plan**

The biostatistics department will handle the randomization and use adaptive randomization to promote equal numbers of men and women in each cell and to promote similar BMI across the groups.

The primary outcome variable is body weight change, represented as kg and percent change. All other variables are secondary and will be analyzed using a similar statistical approach. Repeated mixed linear models will be used to determine if change in the outcome variables differs among the groups. Covariates will include the baseline value of the outcome, sex, and race. Additional variable selection in the models will be determined through model fit statistics such as AIC.

Two sources of body weight data are obtained – weights collected in the clinic at baseline and week 12, and weights collected at the 12 intervention sessions. Both sources of data will be analyzed, though the presence of only two clinic weights means that analysis of the clinic weights will be a completers' analysis. The weekly weight data, however, will be analyzed using an intent-to-treat approach, and all participants' data will be analyzed who have a weight from their first and at least one subsequent intervention visit. Sensitivity analysis will be conducted to determine how the two methods effects the results.

The primary models will be a mixed effect model that accounts for the correlation of the subject over time modeling. Least square means based on the estimates from the mixed effect model will be used to test for differences of weight change between groups. Normality of the responses will be checked based on the Shapiro-Wilk test. Heterogeneity of variance effects for genders for each of the treatments will be analyzed first as potential subgroups.

Hypothesis 1 will test if participants assigned to the diet that corresponded to their genotype lost more weight than those assigned to a diet inconsistent with their genotype.

- H1: Weight loss in Cells A and D (combined) in Table 1 was significantly larger than weight loss in Cells B and C (combined).

Hypothesis 2 will analyze the fat responders and carbohydrate responders separately.

- H2a: Fat responders lost more weight on the high-fat diet (Table 1, Cell A) vs. the high-carbohydrate diet (Cell B), and
- H2b: Carbohydrate responders lost more weight on the high-carbohydrate diet (Table 1, Cell D) vs. the high-fat diet (Cell C).

The *a priori* comparisons noted above will rely on an alpha level of 0.05 for both measures of body weight (kg and %). In addition, we will conduct tests with alpha equal to 0.05 to determine if baseline insulin levels and HOMA (homeostatic model assessment) are associated with weight loss and differential weight loss between the groups and diets. Alpha will be adjusted in the analyses of all other variables using the family-wise error rate employing the Holm-Bonferroni method, which is based on the number of p-values less than alpha.

The Report to the sponsor will include data tables for all outcome variables at all assessment visits, as well as tables depicting change on the outcome variables and the associated inferential statistics. Tables depicting participant demographics will also be provided.

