- **Hypothesis 2b:** Carbohydrate responders will lose more weight on the high-carbohydrate diet vs. the high-fat diet.

Carbohydrate and dietary fat responders will be identified *a priori* based on their combined genotypes at pre-determined genetic variants using specific algorithms. Carbohydrate responders and fat responders will be randomized to one of the following two diets:

1. A high-quality high-carbohydrate diet that is rich in whole-grain foods, or
2. A high-quality high-fat diet that is rich in unsaturated fats and oils (Table 1).

**Table 1.** Overview of the study design and expected relative weight loss (double arrows reflect greater expected weight loss). The total number per group is an estimate. We will not close cells to enroll this exact number per group, and the total number of people enrolled will not exceed 154.

	High-Fat Diet	High-Carb Diet
Fat Responder	Cell A n=52 ↓↓	Cell B n=52 ↓
Carb Responder	Cell C n=25 ↓	Cell D n=25 ↓↓

Both diets will last 12 weeks and have the same levels of protein (15% of energy). The high-carbohydrate diet will consist of ~20% of energy from fat and ~65% from carbohydrates. The high-fat diet will consist of ~40% energy from fat and ~45% from carbohydrates. All participants will be assigned an energy intake target that will result in a daily deficit of ~750 kcal, though no energy intake targets below 1,100 kcal/d (women) and 1,300 kcal/day (men) will be prescribed. At the discretion of the PI or MI, modest diet modifications will be allowed if needed for participant safety. Baseline energy requirements will be calculated with the formulas of Mifflin St. Jeor. The Remote Food Photography Method (RFPM) and SmartIntake smartphone app will be used sporadically as needed to facilitate dietary adherence. These are process data and will not be immediately analyzed to quantify dietary intake, though the images can be fully analyzed later. Rather, the food images will be reviewed by the interventionists in near real-time to help the participant select and eat foods consistent with their meal plan.

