### **Power analysis**

This study will plan to obtain data on up to 154 participants in total. During a previous 12-week study that had a similar weight loss strategy, participants lost 5.1 kg with an SD of 3.3 kg. This SD is larger than the SD for between-group differences observed in other studies conducted by the PBRC group, which range from 2.1 to 2.8 kg; therefore, an SD for between-group differences in weight change of 2.8 kg was utilized. The power analysis for the proposed study uses a T-test to determine differences and assumes an alpha level of 0.05 and power  $\geq 0.80$  as acceptable. Weight loss in cells A and D are both expected to be similar in the previous study while the weight loss in cells B and C would have similar but approximately half that effect of the previous study. To detect a 2.0 kg difference in weight change between either A vs. B or C vs. D, this study would have a power of 0.80. A 2.0 kg difference is approximately 2.2% of body weight assuming the mean body mass of participants is 90 kg. Based on the assumptions above, this study has power over 0.95 to test if the diet that corresponded to their genotype lost more weight than those assigned to a diet inconsistent with their genotype.

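### Covariates beyond baseline value, sex and race are left to an open AIC search on the outcome, which can lift the type I error of H2b above 0.05 if it is fitted as a separate model

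*Combined protocol and SAP*

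**What the plan says.** The Data analytic plan sets out a repeated-measures mixed model for weight change and fixes part of its covariate list: "Covariates will include the baseline value of the outcome, sex, and race". The next sentence opens the rest: "Additional variable selection in the models will be determined through model fit statistics such as AIC". It names no candidates, search direction or stopping rule. It does not say whether selection is blind to diet, or whether it is repeated for each hypothesis, each scale (kg, percent) or each source of weights (clinic, intervention visits).

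Two statements describe how the comparisons are made. One is "Least square means based on the estimates from the mixed effect model will be used to test for differences of weight change between groups". The other is "Hypothesis 2 will analyze the fat responders and carbohydrate responders separately". On the significance level, the a priori "comparisons noted above will rely on an alpha level of 0.05 for both measures of body weight (kg and" percent). No allowance is made for model selection.

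The same section says that adaptive randomization will balance sex and BMI. Sex is a fixed covariate and BMI is not.

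**The concern.** A covariate chosen because it fits the outcome in hand lowers the residual sum of squares by more than the one degree of freedom it is charged. If the selected model is then analysed as though chosen in advance, the reported standard error is too small and the p-value too low. The effect grows with the number of candidates and shrinks with sample size, so the carbohydrate-responder comparison (C vs. D, about 50 people) is the most exposed.

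Two further matters do not depend on the size of the inflation. With no candidate list, the primary model is not fully specified before the data are seen. And a randomization balancing factor, BMI, enters the primary model only if a fit statistic happens to favour it.

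**Working it through.** **Inputs.** Cell sizes are from Table 1 (Background): 52 per cell for fat responders, 25 per cell for carbohydrate responders, all estimates, with the limit "the total number of people enrolled will not exceed 154". The Power analysis gives a 2.0 kg difference and, for spread, "an SD for between-group differences in weight change of 2.8 kg was utilized". The fixed covariates and alpha of 0.05 are from the Data analytic plan. Sidedness is not stated; the simulations use two-sided tests. The number of candidates k is not in the documents, so k = 3, 5 and 10 are assumed, with 20 as an extreme.

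Ten is not far-fetched. Table 2 supplies at baseline waist, hip, body fat, blood pressure, heart rate, three questionnaires, glucose and insulin. That is ten before BMI, HOMA or age is counted.

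**Step 1: the plan's own figure.** The plan's value is 0.80, given in the sentence that begins "To detect a 2.0 kg difference in weight change between either A vs. B or C vs. D, this study would have a power of". The noncentrality is δ/(σ√(2/n)).
- C vs. D: 2.0/(2.8 × √(2/25)) = 2.525 on 48 df. Power is 0.801 one-sided and 0.697 two-sided.
- A vs. B: 2.0/(2.8 × √(2/52)) = 3.642 on 102 df. Power is 0.976 one-sided and 0.950 two-sided.
- H1, taken as 77 vs. 77: 0.993 two-sided, in line with the stated figure of over 0.95.

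The 0.80 is therefore the 25-per-cell comparison tested one-sided. The sidedness should be stated, but that is a separate matter.

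**Step 2: how readily AIC admits a useless covariate.** AIC adds a term when n·ln(RSS₀/RSS₁) > 2. For a covariate with no effect, the left side is roughly chi-square on 1 df, so the chance of entry is P(χ²₁ > 2) = 0.157. Ten useless candidates would thus bring in about 10 × 0.157 = 1.6 terms. The simulation brought in 1.7 at 77 per arm, 1.8 at 52 and 2.1 at 25.

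**Step 3: type I error by simulation.** There is no diet effect. Diet, baseline, sex and race are forced in, forward AIC runs over k further baseline covariates, and diet is then tested at two-sided 0.05. The candidates explain 0% or 20% of outcome variance; ranges span both. There were 8,000 trials per setting and 20,000 in three repeated settings. The Monte Carlo standard error near 5% is √(0.05 × 0.95/8,000) = 0.24 points. The last column is a separate 8,000-trial run with candidates of no effect: all 154 people in one model, C vs. D as a contrast.

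| Candidates k | H2b, separate model | H2a, separate model | H1, 77 per arm | H2b, contrast in four-cell model |
|---|---|---|---|---|
| 3 | 5.4–5.8% | 5.2% | 5.1–5.6% | 5.6% |
| 5 | 5.9–6.5% | 5.2–5.6% | 5.1–5.4% | 5.3% |
| 10 | 7.3–7.7% | 6.2–6.4% | 5.1–6.3% | 5.8% |
| 20 | 12.5–12.8% | 7.4–8.0% | 6.7–6.8% | not run |

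With the fixed covariates only, type I error was 4.5–5.6% at all three sizes, nominal within simulation error. Other simulations of this kind gave 4.9% for H2b with 3 candidates, 8.0% for H2b with 10, and 6.5% for H2a with 10. The rounded ranges in the verdict allow for these.

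**Step 4: does the mechanism account for the figure?** For H2b with 10 candidates of no effect, mean residual variance was 0.896 of its true value. The true SD of the diet estimate was 1.109 times the mean reported standard error. Understated residual variance explains 1/√0.896 = 1.056 of that ratio. The rest is extra variation in the estimate from the choice of model, which the reported standard error leaves out. With about 50 − 5 − 2 = 43 residual df the critical value is 2.017. The effective threshold is 2.017/1.109 = 1.819, and P(|t₄₃| > 1.819) = 0.076, which matches the simulated 7.6% for that setting.

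**The case against.** The strongest reply is that the inflation is small or absent in most of the plan, and several parts of that reply stand.

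- A reader might infer that AIC chooses all the primary covariates. It does not: baseline value, sex and race are fixed, and only further variables are open.
- A reader might infer that the 0.05 level fails for all three a priori comparisons. The figures do not support that. H1 and H2a stay near nominal with up to 10 candidates, and with 5 or fewer the H2a excess is at most 0.6 points.
- Separate models for H2 are the natural reading of the text but not the only one. The least-squares-means sentence also allows H2a and H2b to be contrasts in one four-cell model, with residual error drawn from all 154 people. H2b is then about 5–6%.
- The 7–8% figure needs about 10 candidates. The documents give no number, and with 3 candidates the H2b excess is under one point.
- A reader might infer that the search biases the diet estimate. Choosing baseline covariates in a randomized trial does not by itself favour one diet. Bias would need choices made with the diet effect in view, which the documents neither state nor exclude.

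The simulations also use a single endpoint in place of the planned repeated-measures model.

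What survives is that the plan states a positive rule with open candidates and an open criterion, and tests as if the rule had not been used. Nothing in the text limits the candidates or settles which reading of H2 applies.

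**Conclusion.** The concern holds in a limited form. The primary model is not fully pre-specified, and following the plan as written can understate error in its smallest comparison. With H2b fitted as a separate model at about 25 per cell, type I error is about 5–6% with 3 candidates, 6–6.5% with 5 and 7–8% with 10. With up to 10 candidates, H2a is about 5–6.5%, H1 about 5–6%, and H2b as a contrast in one four-cell model about 5–6%.

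These figures rest on an assumed candidate count, forward selection, two-sided tests, the Table 1 cell sizes being met and an ANCOVA stand-in for the mixed model. Repeating selection by scale or weight source, or selecting with the diet effect visible, was not simulated. The case for a change rests as much on the missing specification and the omission of BMI as on the inflation.

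**What to change.** Replace the AIC sentence with a closed list: the primary model adjusts for baseline value, sex, race and BMI, and H1, H2a and H2b all use that list. State whether H2a and H2b are separate models or contrasts in one four-cell model. Limit AIC to the choice of covariance structure, and report any AIC-extended covariate model only as a sensitivity analysis.

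This changes a few lines of the analysis plan. It needs no new measurement, since height and weight are already collected, and no extra participants. The downside is giving up a possible small precision gain from a covariate not foreseen.

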### **Overview and Objective**

A person's genetic code is believed to affect how much weight he/she will lose during diets that vary in carbohydrate and dietary fat content. 'Carbohydrate responders' are hypothesized to lose more weight on diets that are high in carbohydrates, as compared to high in fats. 'Fat responders' are hypothesized to lose more weight on diets that are high in dietary fat, as compared to high in carbohydrates. The purpose of the proposed study is to test these hypotheses in a randomized controlled trial.

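### Success on only one of H2a and H2b cannot separate a diet effect shared by both responder types from a genotype-specific one, and the plan does not tie either to an equal-weight interaction

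*Combined protocol and SAP*

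**What the plan says.** The Overview and Objective opens from the premise that "A person's genetic code is believed to affect how much weight he/she will lose during diets that vary in carbohydrate and dietary fat content". It then states the hypotheses within type: each responder type is expected to lose more on its own diet than on the other.

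The Data analytic plan lists three comparisons on the four cells of Table 1.

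- H1 compares cells A and D combined with cells B and C combined. The weights used in combining are not given.
- H2a is "H2a: Fat responders lost more weight on the high-fat diet (Table 1, Cell A) vs. the high-carbohydrate diet (Cell B").
- H2b is the corresponding comparison of D with C among carbohydrate responders.

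Of the last two the plan says "Hypothesis 2 will analyze the fat responders and carbohydrate responders separately". On error rates, the a priori "comparisons noted above will rely on an alpha level of 0.05 for both measures of body weight", in kg and in percent. Group differences are to be tested with least-squares means from a mixed model.

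The plan names no diet-by-responder-type term. It does not make the reading of H2a or H2b depend on H1, and it does not say how success on one with failure on the other would be interpreted.

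**The concern.** The trial asks whether genotype changes the response to diet. That is a question about a difference between two diet effects: the one in fat responders (A−B) and the one in carbohydrate responders (C−D). H2a looks only at the first and H2b only at the second. If the high-fat diet were somewhat better for everyone, A−B would be positive for a reason unrelated to genotype, and H2a could succeed. The same holds for H2b if the high-carbohydrate diet were better for everyone.

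A significant H2a beside a non-significant H2b does not settle the matter either, because the C and D cells are less than half the size of A and B (25 against 52), so H2b has less power. At stake is what may be concluded from one positive H2 result.

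**Working it through.** **Inputs.** Cell sizes A = B = 52 and C = D = 25 (Table 1, described there as estimates); SD 2.8 kg, target difference 2.0 kg and alpha 0.05 (Power analysis). Sidedness is not stated; two-sided is assumed unless noted. The size of any shared diet effect, d, is not given. The Background calls mean differences between such diets small, so d = 0.5 and 1.0 kg are used, with 1.5 kg as an upper case. Letters denote mean weight loss in each cell.

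**The plan's own figure.** The figure of 0.80 completes this sentence of the Power analysis: "To detect a 2.0 kg difference in weight change between either A vs. B or C vs. D, this study would have a power of".

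- C vs D: SE = 2.8 × √(2/25) = 0.792; 2.0/0.792 = 2.53. Noncentral-t power is 0.80 one-sided and 0.70 two-sided.
- A vs B: SE = 2.8 × √(2/52) = 0.549; 2.0/0.549 = 3.64. Power is 0.98 one-sided and 0.95 two-sided.
- H1 (77 vs 77): two-sided power is 0.993, consistent with the stated value above 0.95.

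So 0.80 is reproduced for the smaller responder type with a one-sided test.

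**How H1 relates to the interaction.** (A−B) − (C−D) = (A+D) − (B+C). With equal weights for the two responder types, H1 is this contrast up to a factor of one half, and a shared diet effect cancels. Pooled by participant, H1 is [52(A−B) + 25(D−C)]/77. With A−B = d and D−C = −d this equals (52−25)d/77 = 0.35d, so about 35% of a shared diet effect passes through.

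**No genotype effect, high-fat diet better by d in both types.** Chance of significance in the predicted direction:

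| d (kg) | d/0.549 | H2a | H2a and H2b | H1 pooled | Equal-weight interaction |
|---|---|---|---|---|---|
| 0.5 | 0.91 | 14.5% | 0.07% | 6% | 2.5% |
| 1.0 | 1.82 | 44% | 0.03% | 12% | 2.5% |
| 1.5 | 2.73 | 77% | below 0.01% | 21% | 2.5% |

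The H1 column uses SE = 2.8 × √(2/77) = 0.451 and ignores the small extra spread from mixing cells. Simulating the pooled test at d = 1.0 gives 11%.

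For a shared high-carbohydrate advantage of 1.0 kg, H2b succeeds about 24% of the time (1.0/0.792 = 1.26).

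**Sensitivity.** At the previous study's SD of 3.3 kg, the H2a figures are 12%, 33% and 63%. With one-sided 0.05 tests and SD 2.8 kg, the normal approximation for H2a gives Φ(0.91−1.645) = 23% at 0.5 kg and Φ(1.82−1.645) = 57% at 1.0 kg, against 5% for the interaction.

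**Power of the interaction.** SE = 2.8 × √(2/52 + 2/25) = 0.964.

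- Plan's pattern, 2.0 kg in both types: 4.0/0.964 = 4.15, power about 0.985 (0.94 at SD 3.3 kg).
- Only one type responds by 2.0 kg: 2.0/0.964 = 2.08, power about 0.54.

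**The case against.** The strongest reply is that the plan already contains the right contrast. H1 comes first among the hypotheses, and with equal weights it is the interaction. Least-squares means from one model would naturally give such weights, and analysing the types separately may mean two contrasts from a single fit. This largely stands: a reader might infer that the trial has no test of genotype-by-diet response, and the documents do not support that. What remains is that the weighting is unstated, the planned responder types are unequal, and nothing links H2 to H1.

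Second, H2a and H2b predict opposite diet directions. A shared diet effect that helps one counts against the other, and both succeed together in under 0.1% of trials. That stands; the problem is confined to success on one alone.

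Third, a reader might infer that a lone H2a success under a shared diet effect is a type I error, or that it would be reported as a genotype finding. Neither follows. H2a as worded would then be literally true, and the plan does not say how such a result would be reported. The gap is that it gives no rule.

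Fourth, the sizes depend on an assumed diet effect. The Background calls such differences small, so the 1.5 kg row should carry little weight.

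Finally, requiring a significant interaction before accepting H2a or H2b would be expensive if only one type responds by 2.0 kg: H2a would fall from 0.95 to 0.54, or H2b from 0.71 to 0.51. That is a good reason not to impose such a gate, and none is proposed here.

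**Conclusion.** The point holds as an improvement to the analysis plan. Success on one of H2a and H2b is evidence of a diet difference within that responder type. It is not, alone, evidence that the types respond differently.

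Under a shared high-fat advantage of 0.5 to 1.0 kg with no genotype effect, H2a succeeds about 15% to 44% of the time. H1 would guard against this fully with equal weights (2.5%) but only partly if pooled by participant (about 6% to 12%).

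These figures rest on SD 2.8 kg, the Table 1 cell sizes, two-sided 0.05 and an assumed diet effect. The leak through pooled H1 depends on the 52 to 25 split and would vanish if the responder types were of equal size. The limit on what H2a or H2b alone can show does not depend on that split.

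**What to change.** In the Data analytic plan:

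1. Fit one model to all participants with diet, responder type and their interaction, and take H2a and H2b as contrasts from it.
2. Define H1 as the equal-weight contrast (A+D) − (B+C), that is, the diet-by-responder-type interaction.
3. Report its estimate, 95% CI and p-value beside H2a and H2b.
4. State that a single positive H2 result is a diet difference within that responder type, and that any claim of genotype-specific response rests on the interaction.

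The cost is wording; no participants, visits or data are added. H2a and H2b keep their own tests and power. Under the plan's own pattern the interaction has power of about 0.985. The downside is that if only one type responds by 2.0 kg, its power is about 0.54, so a genotype-specific claim becomes harder to make. The within-type estimates are still reported in that case.

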The dietary program and intervention materials will be developed and delivered by employees of Pennington Biomedical Research Center (PBRC). Outcome assessors will be blind to diet assignment and genotype pattern. Interventionists will be blind to genotype pattern, but not diet type. To enhance internal validity, participants will not be told if they are carbohydrate or fat responders until after they complete the study. The **primary outcome** variables are weight change (kg and %) over 12 weeks. All other measures are secondary endpoints. The schedule of procedures is provided in **Table 2**.

**Table 2.** Schedule of visits and procedures.

	Orientation	Baseline (Week 0)	Week 6**	Week 12
Location	IBL	Clinic	IBL	Clinic
Consent, eligibility, demographics, medical history form	X			
Height	X			
Weight	X	X	X	X
Genealogy test kit	X			
Waist/hip circumference, bioelectrical impedance analysis, blood pressure, heart rate, Food Craving Inventory, Food Preference Questionnaire, Eating Inventory		X		X
Blood draw: fasting serum glucose, insulin		X		
Randomization		X		
Intervention Satisfaction Survey				X
Diet Personalization Survey (completed after randomization and at week 6 and 12)		X	X	X
* There is no clinic visit at week 6. The week 6 weight will be collected at the participants' intervention visit, where participants will also complete the Diet Personalization Survey. If participants miss this visit, they will complete the Diet Personalization Survey during the next intervention visit.				
** Weight will be collected at each of the 12 intervention visits.				

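### H1, H2a and H2b are each tested at 0.05 on kg and on % change with no order, adjustment or named primary weight source, and the Holm rule for the other variables is misdescribed

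*Combined protocol and SAP*

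**What the plan says.** The Background section gives the primary outcome on two scales: the primary outcome "variables are weight change (kg and %) over 12 weeks". The Data analytic plan repeats this: "The primary outcome variable is body weight change, represented as kg and percent change".

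That section lists three a priori comparisons: H1 (cells A and D against B and C), H2a (A against B) and H2b (D against C). On alpha, it says that these "will rely on an alpha level of 0.05 for both measures of body weight (kg and" percent). Tests of baseline insulin and HOMA are also run at 0.05. For everything else, "Alpha will be adjusted in the analyses of all other variables using the family-wise error rate employing the Holm-Bonferroni method". The plan then describes that procedure as the "Holm-Bonferroni method, which is based on the number of p-values less than alpha".

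There are two weight sources, clinic weights and intervention-visit weights. The plan says "Both sources of data will be analyzed". Because the clinic supplies just a baseline and a week 12 weight, that source is restricted to completers, while the intervention-visit weights are analysed by intent to treat. It adds: "Sensitivity analysis will be conducted to determine how the two methods effects the results". Neither source is named primary. No order of testing, gate, alpha split or all-must-succeed rule is given, and the plan does not say whether tests are one- or two-sided.

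**The concern.** The plan recognises multiplicity, because it adjusts the secondary variables, but it exempts its main comparisons. Support for genotype-matched diets could be claimed from any one of six tests, or from the more favourable weight source, since nothing fixes in advance which result decides the question. The 0.05 then describes each test and not the conclusion drawn from the set.

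The Holm sentence is a second, separate fault. Holm's thresholds depend on how many tests are in the family, significant or not. A rule driven by the count of small p-values does not protect the secondary family.

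**Working it through.** **Inputs from the documents.** Planned cells A = B = 52 and C = D = 25 (Table 1, Background). Alpha 0.05, effect 2.0 kg, SD 2.8 kg, and SD 3.3 kg in the previous study (Power analysis).

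**Inputs assumed.** Correlation between kg and % test statistics 0.90-0.98; between weight sources 0.80-0.95. The documents give neither.

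**1. The plan's own figures.** Two-sample t-test, 2.0 kg, SD 2.8, alpha 0.05:

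| Comparison | n per side | One-sided | Two-sided |
|---|---|---|---|
| C vs D | 25 | 0.801 | 0.697 |
| A vs B | 52 | 0.976 | 0.950 |
| H1 | 77 | 0.997 | 0.993 |

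The stated 0.80 matches the smaller pair only with a one-sided test. The stated power above 0.95 for H1 holds either way. Sidedness is therefore a real ambiguity.

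**2. Three hypotheses, one scale, one source.** H2a and H2b use different participants, so their statistics are independent under the null, and those two alone give 1 − 0.95² = 0.0975. H1 is their combination, Z(H1) = √(104/154)·Z(H2a) + √(50/154)·Z(H2b). Adding it by simulation gives 0.114 two-sided and 0.109 one-sided. This step needs only the cell sizes.

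**3. Adding scales and sources.** Simulated chance of at least one significant test under the global null:

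| Family | Two-sided, either direction | Two-sided, hypothesised direction only | One-sided 0.05 |
|---|---|---|---|
| 3 tests | 0.114 | 0.058 | 0.109 |
| 6 tests (kg and %) | 0.13-0.16 | 0.07-0.08 | 0.13-0.15 |
| 12 tests (both sources too) | 0.17-0.23 | 0.09-0.12 | 0.15-0.21 |

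The nominal per-test rate is 0.05 in the first and third columns and 0.025 in the second.

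**4. The Holm sentence taken literally.** Let k be the number of p-values below 0.05, and compare the smallest with 0.05/k. Whenever k = 1 the test is rejected automatically. With 10 independent null tests that alone has probability 10 × 0.05 × 0.95⁹ = 0.315. In full, for 10, 15 and 20 null tests with between-test correlation 0 or 0.3, the family-wise error is about 0.32-0.57. Correct Holm gives 0.044-0.049.

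**5. What a remedy costs.** One scale, one source, two-sided tests, normal approximation:

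| Who benefits by 2.0 kg | SD | Test | Unadjusted | Holm (m = 2), no gate | Holm after H1 gate |
|---|---|---|---|---|---|
| Both groups | 2.8 | H2a | 0.95 | 0.94 | 0.94 |
| Both groups | 2.8 | H2b | 0.71 | 0.71 | 0.71 |
| Both groups | 3.3 | H2a | 0.87 | 0.83 | 0.83 |
| Both groups | 3.3 | H2b | 0.57 | 0.55 | 0.55 |
| Carbohydrate responders only | 2.8 | H2b | 0.71 | 0.61 | 0.26 |
| Carbohydrate responders only | 3.3 | H2b | 0.57 | 0.46 | 0.18 |
| Fat responders only | 2.8 | H2a | 0.95 | 0.92 | 0.83 |
| Fat responders only | 3.3 | H2a | 0.87 | 0.80 | 0.68 |

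With carbohydrate responders alone benefiting at SD 2.8, H1 itself has power of only 0.30, so the gate usually stays shut. Under the global null, the gated scheme holds the joint error over all three hypotheses at 5.0%. With H1 at 0.05 and ungated Holm on H2a and H2b, the same simulation gives about 8%.

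**The case against.** The strongest reply is that the three hypotheses are few, pre-specified and closely related, that kg and % are nearly the same measurement, and that whether such a set needs joint control is partly judgement. The plan also nowhere claims a 5% family-wise rate, so no stated figure is contradicted. Much of this stands: the fault is missing control and a missing primary, not a wrong number. But the correlations are already in the rates above, and the 11% floor does not depend on the second scale or source.

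Three stronger readings are tempting, and the documents do not support them.

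- **Twelve primary tests.** The alpha sentence names only the two scales, and the comparison of sources is called a sensitivity analysis. Six is the better count. The ambiguity over which source leads is real, so 17-23% is an upper case.
- **An 11-23% chance of falsely claiming benefit.** Those rates include results where matched participants lose less weight, whereas all three hypotheses are directional. With two-sided tests the chance of an error in the claimed direction is 6-12%; only one-sided 0.05 testing brings it to 11-21%.
- **A secondary error rate that will actually reach 0.57.** The plan names Holm-Bonferroni and family-wise error, and an analyst using standard software would apply it correctly. The large figure describes the sentence as written, for secondary variables only.

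**Conclusion.** The concern holds in this form. Six a priori tests are each run at 0.05, with no order or adjustment and no primary weight source. The chance of at least one false positive in either direction is about 11% for three hypotheses and 13-16% for six two-sided tests, rising to 17-23% only if both sources count as primary. These figures assume the global null, the planned cell sizes, any single significant test counting as a claim, and the stated correlation ranges. Only the 11% needs no assumed correlation. In the hypothesised direction alone, the inflation is from 2.5% to 6-12% with two-sided tests, or from 5% to 11-21% with one-sided tests.

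The Holm description is wrong as written and should be corrected whatever is decided about the primary family. A reader might infer that gating H2 behind H1 costs almost nothing. That is true only if both responder groups have the 2.0 kg effect, and the plan analyses the groups separately, so an effect in one group only has to be allowed for.

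**What to change.** 1. Correct the Holm sentence: thresholds are set by the total number of tests in the stated family. List the family.
2. Name one scale and one weight source as primary. Make H1 on that outcome the single primary test at 0.05. Report the other scale and source as supportive, without separate claims.
3. State whether tests are one- or two-sided, and align the Power analysis with that choice.
4. Label H2a and H2b as secondary and test them with Holm (m = 2). Decide openly whether to gate them behind H1. The gate holds joint error over all three hypotheses at 5%, but cuts H2b from 0.71 to 0.26 (SD 2.8) or from 0.57 to 0.18 (SD 3.3) if only carbohydrate responders benefit. Without the gate, H2b keeps about 0.61 or 0.46 in that case, but the joint error is not held at 5%.

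Items 1 to 3 cost a few sentences and change no visits, procedures or participant numbers. Item 4 costs about 4 points of power or less if both groups respond, and more if only one does. The choice should be recorded before unblinded data are seen.
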